7.1.6.3.2. Sponsor Responsibility

If a serious unexpected adverse event is believed to be related to the study drug or study procedures, the sponsor will take appropriate steps to notify all investigators participating in sponsored clinical studies of reslizumab and the appropriate regulatory authorities (and IEC/IRB, if appropriate).

In addition to notifying the investigators and regulatory authorities (and IEC/IRB, if appropriate), other measures may be required, including the following:

- altering existing research by modifying the protocol
- discontinuing or suspending the study
- altering the process of informed consent by modifying the existing consent form and informing current study participants of new findings
- modifying listings of expected toxicities to include adverse events newly identified as related to reslizumab

7.1.7. Specific Protocol-Defined Adverse Events

7.1.7.1. Adrenal Insufficiency

Adrenal insufficiency will be treated as an adverse event.

Patients who experience the clinical symptoms of adrenal insufficiency (fatigue, weakness, anorexia, lightheadedness, abdominal pain, nausea/vomiting, myalgia) will be instructed to come to the study center for vital signs and evaluation by a physician if possible. Patients with severe symptoms will be instructed to proceed to the emergency department.

Blood samples will be taken for:

- cortisol level (before iv corticosteroids or oral corticosteroid dose increase if possible)
- calcium level
- sodium, potassium, chloride, glucose, creatinine, carbon dioxide, and blood urea nitrogen (BUN) levels
- CBC with differential

Patients determined to have mild symptoms of adrenal insufficiency may have their OCS dose increased back to the previously effective OCS level (at the investigator's discretion).

Patients determined to have clinically significant adrenal insufficiency will be instructed to (at minimum) double or triple their corticosteroid dose for ≥ 2 days.

Then, based on resolution of symptoms:

- If they recently (≤ 7 days) had a dose reduction, they will be instructed to return their corticosteroid dose to the previously effective OCS level.
- If they have not had a recent dose reduction and another factor precipitated the adrenal insufficiency (eg, infection), they should be treated for the inciting factor before OCS dose reduction.

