2.3.8. Safety Endpoints

Safety endpoints will include the following:

- occurrence of adverse events throughout the study, including the week 32 follow-up visit
- clinical laboratory evaluations of serum chemistry at screening, DoR, and periodically throughout the study
- clinical laboratory evaluations of hematology throughout the study
- vital signs (pulse, body temperature, respiratory rate, and blood pressure) measurements throughout the study
- ECG evaluation at screening and at week 24 or early withdrawal
- physical examination findings, including body weight measurements, throughout the study
- signs and/or symptoms of adrenal insufficiency (OCS withdrawal effects) throughout the study
- concomitant medication usage throughout the study, including the week 32 follow-up visit

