3.1.2. Optimization Period

Patients who meet screening eligibility requirements will enter the optimization period for up to 10 weeks to determine the patient's minimal effective OCS requirement. The patient's previous OCS will be standardized to an equivalent dose and regimen of prednisone to facilitate optimization; the same formulation should be maintained through the end of treatment (EOT)

visit. It is expected that the optimization period will be shorter than 10 weeks for those patients who are at or near their optimal corticosteroid dose at enrollment. The patient's previous non-OCS background asthma controller medications will be continued unchanged throughout the pre-randomization period and the entire study. At the beginning of the optimization period, an asthma symptom diary and electronic peak flow meter will be distributed where the patient will record asthma symptoms, number of reliever bronchodilator inhalations, nighttime awakenings due to asthma requiring rescue inhaler, and AM and PM PEF.

For optimization, the prednisone dose should be reduced at 1-week intervals, according to the algorithm shown in Table 1, for up to 10 weeks, or until there is a worsening of asthma signs and symptoms. Worsening of asthma signs and symptoms should be based on the following:

- FEV1 <80% of the screening value AND/OR
- The physician's global assessment of asthma worsening based on trends in daily diary measures for the past 7 days compared with the week prior, as well as any physical examination signs

When either a lung function or a symptomatic deterioration occurs, the patient will be returned to the previously effective OCS level, which will then constitute the minimally effective dose for the purpose of run-in. If this previously effective dose is no longer effective, the investigator can determine the clinically appropriate minimally effective dose for the purpose of run-in.

Regarding the amount and rate of OCS reduction during dose optimization, in order to provoke a worsening of asthma signs and symptoms within the 10-week, monitored optimization period, OCS reduction should be attempted approximately every 1 week after evaluation in the clinic. The magnitude of OCS reduction will be based on the following Optimization Phase OCS Dose Reduction Algorithm ([Table 1](#)).

Table 1: Optimization Phase Prednisone Dose Reduction Algorithm

Time Course	Oral OCS Dose (mg/day)								
Visit 2 starting dose ^a	40+ ^b	35	30	25	20	15	10	7.5	5

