3.1.4. Treatment Period

Patients continuing to meet eligibility criteria on the day of randomization (day 1, week 0) will be randomly assigned in a 1:1 ratio to receive placebo or reslizumab 110 mg once every 4 weeks

through week 20, followed by an EOT visit at week 24. Patients will begin treatment on day 1 after completing baseline assessments, and they will return to the research facility for outpatient visits every 4 weeks through week 24 (EOT visit) for safety, PK, PD, immunogenicity, and efficacy assessments as applicable.

During the treatment period, the patient will continue his/her usual non-OCS background asthma medication without change; the OCS dose will be tapered per protocol. The treatment periods consist of the following:

- **Induction:** The minimally effective dose of OCS will be maintained, unchanged, during the first 4 weeks of the treatment period to allow sufficient time for any potential treatment effect to become established.
- **OCS reduction:** The minimally effective OCS dose will be reduced per protocol at scheduled clinic visits from the beginning of week 5 (ie, end of the induction period) through week 20, as long as all 5 criteria in [Table 2](#) are met and there are no clinical manifestations of adrenal insufficiency. These 5 eligibility criteria assure that the patient's asthma control is not significantly worsened compared to baseline. The last possible dose reduction can occur at week 20. The algorithm for OCS reductions during the treatment period is given in [Table 3](#).

If the OCS dose could not be decreased, it should be held constant, or may be increased to a previous level, at the investigator's discretion, until dose reduction criteria are met.

- **Maintenance:** OCS will be held stable from week 20 through EOT at week 24.

Table 2: Eligibility Criteria for Scheduled Oral Corticosteroid Reductions During the Treatment Period (Must Meet All)

1	Forced expiratory volume in 1 second (FEV ₁) ≥80% of baseline ^a
2	AM PEF ≥80% of baseline mean AM PEF on at least 5 of the 7 days preceding the visit
3	Mean nighttime awakenings due to asthma requiring rescue inhaler over the preceding 7 days ≤ 150% increase over the baseline period
4	Reliever bronchodilator inhaler use does not exceed 150% of the baseline inhaler use per 24 hours on more than 2 of the preceding 7 days
5	No increase in OCS dose since the previous visit ^b

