^a Baseline for clinic visit measures (FEV₁) is the DoR value. Baseline for diary measures is the average over the 7 days before DoR.

^b If a dose increase results in a return to the previous dose, then it is acceptable to attempt dose decrease again at the investigator's discretion.

AM=morning; DoR=date of randomization; FEV₁=forced expiratory volume in 1 second; PEF=peak expiratory flow; OCS=oral corticosteroid.

Table 3: Oral Corticosteroid Decrements During the Treatment Period

Time Course	Oral OCS Dose (mg/day)								
Optimized OCS dose	40	35	30	25	20	15	10	7.5	5
1st reduction	30	25	20	15	10	10	7.5	5	2.5
+ 4 weeks	20	15	10	10	7.5	7.5	5	2.5	0
+ 4 weeks	10	10	5	5	5	5	2.5	0	
+ 4 weeks	5	5	2.5	2.5	2.5	2.5	0		
+ 4 weeks	2.5	2.5	0	0	0	0			

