Procedures and assessments	Pretreatment		V12 Start run-in	Double-blind treatment period (visit/week)							Follow-up	Late follow-up
	V1	V2-V11		V13 ^a	V14 ^a	V15 ^a	V16 ^a	V17 ^a	V18 ^a	V19 ^a	V20	V21
	Start of screening period	Standardize and optimize maintenance OCS ^{abc}										
	Week -14 ^d	Between weeks -12 and -3		W -2	DoR	W4±7d	W8±7d	W12±7d	W16±7d	W20±7d	W24±7d/ EOT/ early termination	W32/EOT + 8w ±7d
AQLQ+12				X	X	X	X	X	X	X		
ACQ-6				X	X	X	X	X	X	X	X	
EQ-5D				X						X		
St. George’s Respiratory questionnaire				X			X			X		
Assess CAEs and related HCU ^r				X	X	X	X	X	X	X		
Phadiatop allergy test				X								
OCS withdrawal effects inquiry ^s			X	X	X	X	X	X	X	X		
Adverse event inquiry ^t		X	X	X	X	X	X	X	X	X	X	
Concomitant medication inquiry	X	X	X	X	X	X	X	X	X	X	X	

^a The site will contact IWRS at every optimization and treatment visit.

^b The patient’s previous OCS should be switched to an equivalent, standardized prednisone formulation. Optimization may occur once OCS standardization is complete.

^c Attempts at OCS reduction should be made at 1-week intervals, for up to 10 weeks or until there is a worsening of asthma signs and symptoms, to help determine the patient’s lowest effective OCS dose. This period may be shortened if the lowest effective dose is achieved sooner. Eosinophil counts during the optimization period or at the week -2 visit may be considered in order to meet the eosinophil inclusion criteria for this study. Patients requiring an average daily dose of between ≥5 mg and ≤40 mg may proceed to run-in and maintained without change during run-in.

^d The screening period (between V1 and V2) can be less than 2 weeks if all of the screening inclusion criteria are met sooner. It is understood that not all procedures can be completed on the same day. In particular, the patient may need to return to satisfy the medication hold for screening pre bronchodilator FEV1 and reversibility testing.

Clinical Study Protocol with Amendment 02

- ^e Verify that essential screening inclusion criteria for asthma are met before entering optimization.
- ^f Reversibility testing is most conveniently performed at the same visit as the screening, pre-bronchodilator spirometry. All patients must undergo reversibility testing, even if they are submitting historical reversibility or methacholine provocation results to support inclusion criterion e. Reversibility testing may be repeated once, within the 2-week screening period.

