3.16.2. Procedures Before Study Drug Treatment

3.16.2.1. Procedures During the Optimization Period (Weeks –12 through –3 [Visits 2 through 11])

- Verify that essential screening inclusion criteria for asthma are met before entering optimization
- Perform hematology tests (CBC with differential) if the inclusion criterion of an eosinophil count of 300/ μ L or greater was not met at screening
- Perform brief physical examination
- Perform vital signs assessments
- Provide and collect PEF meter
- Provide/collect electronic asthma control diary; reinforce diary and PEF compliance
- Attempt OCS reduction
- Concomitant medication inquiry
- Adverse event inquiry

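### Adrenal-insufficiency safeguards do not match the two steroid tapers: weekly optimization has no scheduled withdrawal inquiry or adrenal hold, and one response instruction cannot be applied at 0 mg

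*Protocol*

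**What the plan says.** **Monitoring.** Protocol 2.3.8 lists as a safety endpoint "signs and/or symptoms of adrenal insufficiency (OCS withdrawal effects) throughout the study". Section 3.8 says the safety measures apply throughout and are evaluated at the Table 5 time points. The Table 5 row "OCS withdrawal effects inquiry" is marked at V12 to V19 and is blank at V2 to V11. SAP Table 4 repeats it. The visit lists agree: 3.16.2.1 (optimization) includes "Attempt OCS reduction" but no withdrawal assessment, while 3.16.2.2 (V12) and 3.16.3.1.1 (treatment visits) include one.

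**Taper rules.** In optimization, 3.1.2 says "the prednisone dose should be reduced at 1-week intervals", continuing "for up to 10 weeks, or until there is a worsening of asthma signs and symptoms". Worsening is judged on FEV1 and/or the physician's global assessment of asthma. In the treatment period, 3.1.4 permits a reduction only if the Table 2 criteria "are met and there are no clinical manifestations of adrenal insufficiency".

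**Response.** Section 7.1.7.1 is not limited to any study period. Mild symptoms may be met by a return to the previously effective dose, at the investigator's discretion. For the next tier it says: "Patients determined to have clinically significant adrenal insufficiency will be instructed to (at minimum) double or triple their corticosteroid dose", for at least 2 days. After that there are two branches. One is for a dose reduction within the past 7 days. The other is for no recent reduction together with another precipitating factor. Severe symptoms go to the emergency department.

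**Target dose.** Table 3, "Oral Corticosteroid Decrements During the Treatment Period", runs down to 0 mg for most starting doses, and stopping OCS altogether is a secondary endpoint.

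**The concern.** Adrenal insufficiency is the foreseeable harm of the trial's own procedure, the steroid taper. The protocol treats a dedicated inquiry as worthwhile at eight visits (V12 to V19) but omits it at up to ten visits where the dose falls fastest per week, and gives no reason. The symptoms listed in 7.1.7.1 (fatigue, weakness, nausea, myalgia and others) are non-specific, and an open-ended adverse event question can miss them.

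The rules also conflict. A patient in optimization with adrenal symptoms and stable asthma has not met the stopping condition of 3.1.2, so the text has the next weekly cut still to be attempted. Section 7.1.7.1 allows or directs an increase for the same patient. Two sites could act in opposite ways and both be following the protocol.

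In the treatment period, the instruction for clinically significant cases depends on the current dose, and the taper aims to bring that dose to zero.

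**Working it through.** No figure in the plan bears on this point, so there is none to reproduce. The check is arithmetic on Protocol Tables 1 and 3 and a comparison of the rules.

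**1. Relative speed of the two tapers.** Inputs: Table 1 steps are 1 week apart; Table 3 steps are nominally 4 weeks apart (weeks 4, 8, 12, 16 and 20). The time from first reduction to 2.5 mg is the number of later steps needed times the interval. Ratio = treatment weeks / optimization weeks.

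| Start (mg) | Optimization (weeks) | Treatment (weeks) | Ratio |
|---|---|---|---|
| 40 | 8 | 16 | 2.0 |
| 35 | 7 | 16 | 2.3 |
| 30 | 6 | 12 | 2.0 |
| 25 | 5 | 12 | 2.4 |
| 20 | 4 | 12 | 3.0 |
| 15 | 3 | 12 | 4.0 |
| 10 | 2 | 8 | 4.0 |
| 7.5 | 1 | 4 | 4.0 |
| 5 | 0 | 0 | single step in both |

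Optimization is 2 to 4 times faster wherever the ratio is defined. The largest single cut is nevertheless bigger in treatment (10 mg against 5 mg).

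**2. The dose multiple at 0 mg.** 2 × 0 = 0 and 3 × 0 = 0. The Table 3 columns that end at 0 mg are 30, 25, 20, 15, 10, 7.5 and 5, which is 7 of 9; the 40 and 35 mg columns end at 2.5 mg. If every step is taken from week 4:

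| Start (mg) | 0 mg reached at week | Weeks at 0 mg by week 24 |
|---|---|---|
| 5 | 8 | 16 |
| 7.5 | 12 | 12 |
| 10 | 16 | 8 |
| 15 to 30 | 20 | 4 |

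**3. The follow-on branches in 7.1.7.1.**

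| | Other precipitant | No other precipitant |
|---|---|---|
| Reduction within 7 days | branch 1 | branch 1 |
| No reduction within 7 days | branch 2 | no branch |

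One cell of four is empty. With strictly weekly cuts in optimization, every onset between cuts falls in the first row. The empty cell can arise once the dose has been stable for more than 7 days, as it is for most of each 4-week treatment interval.

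**4. The hold rules side by side.** Section 3.1.4 makes the absence of adrenal manifestations a condition for a cut. Section 3.1.2 names no adrenal condition. Section 7.1.7.1 applies to both periods and points towards a dose increase. For optimization, 3.1.2 and 7.1.7.1 therefore give different answers, and nothing states which governs.

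**The case against.** The strongest reply is that patients in optimization are not unwatched. V2 to V11 carry an adverse event inquiry, a brief examination and vital signs. Adverse events are collected from consent, clinically significant adrenal insufficiency is named as an example in 7.1.1, and the CRF has a yes/no field for relation to OCS reduction (7.1.5). Unscheduled visits include an adrenal evaluation. Section 3.1.2 says reductions should be attempted about weekly after clinic evaluation, which leaves room for judgement, and 7.1.10 allows case-by-case departures. All of this stands and limits the seriousness. It does not explain why the targeted inquiry starts only after the faster taper, and it does not settle which section governs the next cut.

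Four stronger readings are tempting but unsupported:

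- **That the adrenal response operates on only 7 of every 28 days.** It does not. Evaluation, the mild-symptom option, emergency referral and the double-or-triple step have no 7-day limit. The limit belongs to one follow-on branch.
- **That a patient at 0 mg would be left without steroid.** The instruction is worded as a minimum, the section mentions iv corticosteroids and emergency referral, and branch 1 can still be applied soon after a cut. The defect is that one sentence cannot be applied as written.
- **That V20 also needs the inquiry.** Vital signs and physical examination are likewise described as throughout the study but are not marked at V20, so the phrase does not mean every visit. Scheduled reductions end at week 20, and V20 has an adverse event inquiry.
- **That the primary endpoint's baseline is biased.** Optimization precedes randomization, so an adrenal-driven stop cannot depend on treatment arm. Baseline OCS dose is also a stratification factor and covariate, and the documents give no frequency for such stops.

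**Conclusion.** The point holds in three limited parts. First, the targeted withdrawal inquiry and an explicit adrenal hold are both absent from the taper that is 2 to 4 times faster, and 3.1.2 is not reconciled with 3.1.4 and 7.1.7.1. Second, the instruction for clinically significant adrenal insufficiency yields 0 mg at a dose that 7 of 9 Table 3 columns reach, as early as week 8. Third, one of the four follow-on combinations has no instruction.

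The speed range assumes nominal visit spacing, and the week-8 figure also assumes that every scheduled reduction is taken. With ±7-day windows the treatment intervals can run from 14 to 42 days. How often any of these cases would arise cannot be estimated from the documents. The sponsor should correct this, mainly because the remedy is cheap and concerns the safety of a study procedure. No effect on the primary comparison is claimed.

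**What to change.** 1. Mark the existing OCS withdrawal effects inquiry at V2 to V11 in Protocol Table 5 and SAP Table 4, and list it in Protocol 3.16.2.1.
2. Record on the CRF whether optimization stopped for asthma or for adrenal reasons.
3. Reconcile 3.1.2 with 3.1.4 and 7.1.7.1 on what happens to a scheduled reduction when adrenal manifestations are present.
4. Reconcile 7.1.7.1 with Table 3 for patients at 0 mg, and for the case that neither follow-on branch covers.

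The clinical content of items 3 and 4 is for the sponsor's physicians; no dose or rule is proposed here. The cost is protocol and SAP wording, one CRF field and a few minutes at visits already held. A possible downside is that some patients may stop optimization earlier.

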7.1.7.2. Protocol-Defined Adverse Events for Expedited Reporting to Teva

For the purposes of this protocol, the following are considered protocol-defined adverse events for expedited reporting to Teva: anaphylaxis, newly diagnosed malignancy, opportunistic infection, and parasitic helminth infection. Protocol-defined adverse events for expedited reporting can be either serious or nonserious according to the criteria outlined in Section 7.1.6.1. The process for reporting a protocol-defined adverse event for expedited reporting is the same as that for reporting a serious adverse event (see Section 7.1.6.3). A list of potential opportunistic infections is found in [Appendix I](#).

7.1.7.3. Specific Adverse Event Case Report Form Capturing

7.1.7.3.1. Anaphylaxis/Hypersensitivity Reactions Case Report Form

Information about all suspected anaphylaxis events will be recorded on the Suspected Anaphylaxis/Hypersensitivity Reactions CRF, including the investigator's assessment if the event followed the definition of anaphylaxis based on the diagnostic criteria as outlined by the 2006 Joint NIAID/FAAN Second Symposium on Anaphylaxis ([Sampson et al, 2006](#)) ([Appendix H](#)). The Anaphylaxis/Hypersensitivity Reactions CRF should be initiated in real time (along with vital sign assessment) for events occurring after study drug administration in the clinic or as soon as possible for suspect events outside the clinic.

7.1.7.3.2. Creatine Phosphokinase/Muscular Adverse Events CRF

Potentially clinically significant creatine phosphokinase (CPK) elevations (with or without associated symptoms) or myalgia/muscle symptoms will be recorded as an adverse event and documented using the potentially clinically significant CPK/myalgia case report form. A potentially clinically significant CPK is defined as $\geq 3.1 \times$ the upper limit of normal (ULN) (Grade 3 based on the Food and Drug Administration [FDA] “Guidance for Industry Toxicity Grading Scale for Healthy Adult and Adolescent Volunteers Enrolled in Preventative Vaccine Clinical Trials”).

If a potentially clinically significant CPK level ($\geq 3.1 \times$ ULN) occurs, the patient should attend an unscheduled visit for a physical examination and additional testing if indicated per investigator judgement. CPK levels will be re-tested at a minimum of every 7 to 10 days until the elevation is resolved, or if agreed with the medical monitor that no further testing is indicated. For $\geq 10 \times$ ULN elevations in CPK, repeat CPK level, urinalysis (including microscopy), serum electrolytes, BUN, and creatinine will be performed as soon as possible after receipt of the CPK result. Further testing of CPK levels should be undertaken as frequently as needed to manage patient care per investigator judgment, but should be at a minimum of every 7 to 10 days as above. Need for repeat urinalysis, serum electrolytes, BUN, and creatinine testing should be determined by the investigator. In addition, need for treatment (eg, administration of iv fluids and urine alkalinization) should be considered by the investigator.

In cases deemed by the investigator to be treatment-related elevations in CPK $\geq 10 \times$ ULN (eg, potentially rhabdomyolysis), study drug discontinuation should occur at least until CPK normalization or longer based on investigator clinical assessment.

